Subjects who agreed to participate had baseline testing performed to determine eligibility with inclusion/exclusion criteria. For subjects who participated in the FUEL study and continued on to this extension study, safety laboratory results from FUEL were accepted as meeting the inclusion criteria for FUEL Extension. For De Novo subjects, the baseline visit consisted of 2 parts, baseline testing and study drug initiation. These parts may have been combined into a single day or split into 2 days so long as the duration between the visits was no more than 7 days. Safety laboratory testing and pregnancy testing for female participants were performed. After safety laboratory testing, subjects performed an exercise test to maximal effort to be eligible for study drug initiation.

All enrolled subjects were provided with udenafil, at a dose of 87.5 mg BID, for the duration of the study. The first dose of study drug was administered at the clinic (Visit 1). Approximately 2 hours (\pm 30 minutes) post dosing, resting heart rate and blood pressure were measured, and the subject performed a self-limited 6-minute walk. A repeat heart rate and blood pressure were measured immediately following and approximately 2 hours (\pm 30 minutes) following the 6-minute walk. Subjects who had a drop in systolic blood pressure >20 mmHg from the pre- to post-6-minute walk measurement, or had a drop in systolic blood pressure below the 5th percentile for age, were excluded from receiving any further study drug. Continuing subjects were dispensed their initial supply of study medication and instructed to take 1 tablet orally BID.

Methodology (continued):

All subjects returned to the clinic at Week 52. In addition to clinic visits, study coordinators contacted each subject by telephone the day after the baseline visit to discuss any adverse events (AEs). Subjects were also contacted by telephone at Weeks 1, 2, 3, 4, 8, 13, 17, 21, 30, 34, 39, 43, and 47 to ensure the study drug was well tolerated, to monitor study drug adherence, record AEs and concomitant medications, and offer pregnancy counseling, if needed. Subjects were encouraged to notify the study coordinator between scheduled contact dates with any new onset symptoms or complications.

For subjects continuing in FUEL Extension beyond Week 52, telephone contact occurred monthly and 30 and 90 days following study drug discontinuation to ensure the study drug was well tolerated and record AEs.

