
Statistical methods at interim analysis: The Safety population included all subjects who took at least 1 dose of study drug. The Efficacy population included all enrolled subjects who had baseline and Week 52 exercise capacity data for which site-based data quality assurance process was complete at data cut-off.

Three treatment groups were defined:
 
• Udenafil-Udenafil, which included subjects who received udenafil in the FUEL and FUEL Extension studies• Placebo-Udenafil, which included subjects who received placebo in the FUEL study and udenafil in FUEL Extension• De Novo: Subjects who did not participate in the FUEL study and received udenafil in FUEL Extension

For efficacy and safety summaries, the Placebo-Udenafil and De Novo groups were combined (denoted as Placebo/De Novo-Udenafil).

All summaries were descriptive. Descriptive statistics for categorical endpoints included the number and percent of subjects in each treatment group and category. Quantitative endpoints were summarized for each treatment group with the mean, median, standard deviation, minimum value, and maximum value. Missing data were not imputed.

Baseline was defined as the last measurement before receipt of udenafil in FUEL Extension. For the Udenafil-Udenafil group, change to Week 52 of FUEL Extension measures change in exercise capacity between 26 weeks and 78 weeks of udenafil treatment. This change represents persistence of initial effectiveness beyond 26 weeks. For the Placebo-Udenafil and De Novo groups, change to Week 52 of FUEL Extension measures change in exercise capacity from pre-udenafil to following 52 weeks of udenafil treatment.

Statistical methods (continued):

For each efficacy endpoint, descriptive statistics were summarized for baseline, Week 52, and Week 52 change from baseline. A 2-sided, 95% confidence interval was calculated for change from baseline for each group.

Safety analyses were descriptive with no formal hypothesis testing. All AEs were classified by the Medical Dictionary for Regulatory Activities with respect to system organ class and preferred term. Subject incidence of all treatment-emergent adverse events (TEAEs), and TEAEs that are treatment-related, serious, serious treatment-related, and any TEAE leading to study discontinuation were tabulated. Number (%) of subjects who were hospitalized, had a cardiac transplant, or died were tabulated.

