Subjects returned to the clinic at Week 26 (study completion/early termination). In addition to clinic visits, study coordinators contacted each subject by telephone the day after the baseline visit to discuss any adverse events (AEs). Subjects were also contacted by telephone at Weeks 1, 2, 3, 4, 8, 13, 17, and 21 to ensure the study drug was well tolerated, to monitor study drug adherence, record AEs and concomitant medications, and offer pregnancy counseling, if needed. Subjects were encouraged to notify the study coordinator between scheduled contact dates with any new onset symptoms or complications.

[figure not shown]
In-clinic study visits included assessments of safety (AEs, concomitant medication use, vital signs, and clinical safety laboratory evaluations), efficacy (exercise testing, echocardiogram, EndoPAT®, BNP, and quality of life measurements), and PK.

The duration of study drug dosing was 26 weeks. When an individual subject completed the study, the subject's primary cardiologist was notified, and the study drug was stopped. All subjects were invited to participate in an open-label, 12-month safety extension study of udenafil. Any subject declining participation in the extension study was to be followed for 90 days at Weeks 30, 34, and 39 for any additional AEs.

Subjects were given the opportunity to participate in the heart rhythm-monitoring subset of FUEL until a total of 25% of all randomized subjects had been included. Heart rhythm monitoring included a 7-day baseline monitor and a 3-day steady state monitor, as described in [Section 9.5.1.2.6](#).

The study design is displayed in [Figure 1](#). The overall schedule of assessments is provided in [Table 2](#). [Table 3](#) presents procedures performed before and after the first dose of study drug in the clinic at Visit 1.

Figure 1: Study Design

AE=adverse event; BNP=brain natriuretic peptide; BP=blood pressure; ECG=electrocardiogram; echo=echocardiogram; EST=exercise stress test; FUEL=Fontan Udenafil Exercise Longitudinal Assessment Trial; LV=left ventricular; min=minute; OLE=open-label extension; PK=pharmacokinetic; RV=right ventricular; yrs=years

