9.8.2.4 Changes to Address Refusal to File Letter

The MedDRA coding of some adverse events was revised for consistency per request by the Food and Drug Administration.

The definition of TEAEs was changed from events that began after receipt of randomized study drug to events that began after receipt of randomized study drug and within 90 days after last dose of study drug.

10 Study Subjects

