Source: [Table 14.1.3](#)

Program: [T_14_1_3.sas](#)

The percentage of subjects who discontinued study drug was low and similar between treatment groups (12 [6.0%] of udenafil-treated subjects, 9 [4.5%] of placebo-treated subjects). Six subjects (4 udenafil, 2 placebo) were prematurely discontinued from study drug

by physician decision and 11 subjects (6 udenafil, 5 placebo) were prematurely discontinued from study drug by subject (ie, participant) decision. Three udenafil-treated subjects discontinued study drug due to a serious TEAE and all other subjects discontinued study drug due to other reasons.

The profile of study discontinuations was similar to study drug discontinuations. Subject disposition is summarized in [Table 5](#). Subjects who discontinued from study are identified in [Listing 16.2.1](#), and subjects who discontinued study drug are identified in [Listing 16.2.1.2](#).

Table 5: Subject Disposition

Disposition	Udenafil (N=200) n (%)	Placebo (N=200) n (%)	Total (N=400) n (%)
Randomized and treated	200 (100.0)	200 (100.0)	400 (100.0)
Prematurely discontinued study drug	12 (6.0)	9 (4.5)	21 (5.3)
Lost to follow-up	2 (1.0)	2 (1.0)	4 (1.0)
Physician decision to permanently stop drug	4 (2.0)	2 (1.0)	6 (1.5)
Due to serious TEAE	3 (1.5)	0	3 (0.8)
Due to other reasons	1 (0.5)	2 (1.0)	3 (0.8)
Participant decision to permanently stop drug	6 (3.0)	5 (2.5)	11 (2.8)
Due to other reasons	6 (3.0)	5 (2.5)	11 (2.8)
Discontinued study	12 (6.0)	6 (3.0)	18 (4.5)
Lost to follow-up	7 (3.5)	4 (2.0)	11 (2.8)
Physician decision to discontinue study	1 (0.5)	0	1 (0.3)
Due to serious TEAE	1 (0.5)	0	1 (0.3)
Due to other reasons	0	0	0
Subject decision to discontinue study	4 (2.0)	2 (1.0)	6 (1.5)
Due to other reasons	4 (2.0)	2 (1.0)	6 (1.5)
Completed study ^a	188 (94.0)	194 (97.0)	382 (95.5)
Continued in extension study	126 (63.0)	124 (62.0)	250 (62.5)

TEAE=treatment-emergent adverse event

a As defined by status change form

Source: [Table 14.1.2](#)

Program: [T_14_1_2.sas](#)

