2.0 Overall Study Design

This study is a randomized, double-blind, 26-week, multicenter trial of udenafil (87.5 mg, twice daily) versus placebo on aerobic exercise performance as measured by change in minute oxygen consumption (VO₂) at maximum exercise effort (maximal VO₂) from baseline to six months in adolescent survivors of the Fontan procedure.

Eligible subjects will be randomly assigned to one of two treatment groups (udenafil or placebo) by a web-based system at the data coordinating center. Randomization will occur within strata defined by ventricular morphology (single left versus single right or mixed).

The first dose of randomized study drug will be administered at the clinic (Visit 1) and outpatient dosing will be used for the remainder of the 26-week study. Subjects will return to the clinic for assessments at 2 weeks (Visit 2), 13 weeks (Visit 3), and 26 weeks (Visit 4) or study completion after initiation of study drug dosing.

Maximal VO₂ will be assessed at Visits 1 and 4 (or study completion) using a braked cycle ergometer following a ramp protocol. Additional assessments will include ventricular performance as measured by echocardiogram, endothelial function assessment with EndoPat®, and serum brain-type natriuretic peptide (BNP) level. Quality of life will be assessed with the Pediatric Quality of Life Inventory (PedsQL), Pediatric Cardiac Quality of Life Inventory (PCQLI), and the Habitual Activity Estimation Scale (HAES).

Blood samples for pharmacokinetic assessments of udenafil and its primary metabolite will be obtained after the first dose of randomized study drug and at Visit 4 (or study completion). Safety will be monitored by adverse event reports, resting vital signs, and clinical laboratory tests.

When an individual subject completes the study, the subject's primary cardiologist will be notified, and the study drug will be stopped; there will be no need to wean subjects off the study drug. Subjects will not be told which drug they received until all recruitment and follow-up is completed per-protocol. All subjects will be invited to participate in an open-label, 12-month safety extension trial of udenafil.

CONFIDENTIAL

The blind for the study will be broken when the later of the following 2 events occur and all database queries have been resolved:

- Visit 4 is completed for the last subject who enters the safety extension trial, or

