6.5.2 Adverse Events

The number and proportion of subjects who report treatment-emergent adverse events (TEAEs) will be summarized for each treatment group. A TEAE is an event that begins after receipt of randomized study drug. All adverse events will be classified by MedDRA with respect to system organ class and preferred term.

The adverse event profile will be characterized with intensity and relationship to study drug (related, unrelated, unknown). Related adverse events will be defined as events considered possibly or probably related to treatment by the investigator. Events with unknown severity or relationship will be counted as unknown. The incidence of serious adverse events will be summarized similarly.

Subjects who report the same preferred term on multiple occasions will be counted once for the preferred term: under the highest severity when summarized by severity and under the closest relationship to study drug when summarized by relationship. If a subject reports multiple preferred terms for a system organ class, the subject will be counted only once for that system organ class.

Proportions for adverse events that are gender-specific (e.g., dysmenorrhea) will be based on the number of subjects from that gender.

The number and percentage of subjects who experience TEAEs will be summarized by treatment group for the following:

- By system organ class and preferred term
- By intensity (mild, moderate, or severe/life threatening/death), system organ class, and preferred term
- By relationship to study drug (not related or related), system organ class, and preferred term
- By weight tertile, system organ class, and preferred term
- By age tertile, system organ class, and preferred term
- Serious adverse events (SAEs) by system organ class and preferred term
- SAEs by relationship to study drug (not related or related), system organ class, and preferred term
- SAEs by weight tertile, system organ class, and preferred term
- SAEs by age tertile, system organ class, and preferred term

CONFIDENTIAL

- Adverse events resulting in discontinuation of study drug by system organ class and preferred term

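### The TEAE window does not close at the first open-label udenafil dose, so any such event reaching the FUEL dataset from the 124 placebo entrants would count under placebo, although none is shown to have done so

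*Protocol*

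**What the plan says.** The SAP, section 6.5.2, gives the window a start and no end: "A TEAE is an event that begins after receipt of randomized study drug". Section 9.8.2.4 of the protocol document, which lists changes made to address a refusal-to-file letter, replaces this with "events that began after receipt of randomized study drug and within 90 days after last dose of study drug". Neither text mentions the extension. The only rule that moves a subject to another arm for safety is in the Safety population definition (protocol 9.7.1.1, SAP 6.1). It covers a subject given the wrong drug, not planned passage to open-label drug.

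On the extension, the synopsis says: "All enrolled subjects were provided with udenafil, at a dose of 87.5 mg BID, for the duration of the study". Table 5 (section 10.1) shows 126 udenafil subjects (63.0%) and 124 placebo subjects (62.0%) continuing into it.

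On follow-up after Week 26:
- Section 9.1: "Any subject declining participation in the extension study was to be followed for 90 days at Weeks 30, 34, and 39", for further adverse events.
- SAP section 2.0 ties unblinding to the later of two events. One is that "Visit 4 is completed for the last subject who enters the safety extension trial"; the other is the end of the 90-day follow-up for the last subject who does not enter.
- Table 2 (section 9.5.1) shows adverse event assessment at the Week 30, 34 and 39 calls without limiting it to decliners. The SAP schedule (section 5.0) flags the same entry as done only where applicable.
- Section 9.5.1.2.1 requires a death or other serious event possibly related to study drug to be reported whenever it occurs, even after the subject has stopped drug or left the study.

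**The concern.** A safety comparison against placebo needs the placebo column to hold events that arose on, or shortly after, placebo. For a placebo subject who enters the extension, part or all of the 90 days after the last placebo dose is spent on udenafil. The definition still labels that time as placebo, and no other rule relabels it.

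If such events were counted, known udenafil effects such as headache and flushing would raise the placebo rates and narrow the contrast on which the report's conclusion of good tolerability rests. For common events a few misassigned subjects would hardly show. For serious events they would: Table 24 has serious TEAEs at 14 versus 10 subjects and drug-related serious TEAEs at 4 versus 2.

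**Working it through.** **1. The plan's own figures.** Table 5 reproduces: 124/200 = 62.0%, 126/200 = 63.0%, 250/400 = 62.5%.

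**2. The rule applied by group.**

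| Placebo subjects | Drug taken in the 90 days after the last dose | Scheduled FUEL adverse event collection after Week 26 (section 9.1) | Arm under the definition |
|---|---|---|---|
| Declined the extension | None | Weeks 30, 34, 39 | Placebo |
| Entered the extension (124) | Open-label udenafil from entry | None stated | Placebo |

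The second row is the gap. The label is wrong for any event recorded there, but section 9.1 schedules no FUEL collection for that row.

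**3. Ceiling on the overlap.** I read the last dose of study drug as the last randomized dose. Let g be the days between it and the first open-label dose. The documents do not give g. For the subjects previously on udenafil, the synopsis says that "change to Week 52 of FUEL Extension measures change in exercise capacity between 26 weeks and 78 weeks of udenafil treatment", which suggests g near 0; I treat that as an assumption and show the range.

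Overlap = 124 × (90 − g). The mean placebo time from first to last dose is 182.7 days (Table 23), so the nominal placebo window is 200 × 182.7 + 200 × 90 = 36,540 + 18,000 = 54,540 days.

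| g (days) | Overlap (person-days) | Share of 54,540 |
|---|---|---|
| 0 | 11,160 | 20.5% |
| 30 | 7,440 | 13.6% |
| 60 | 3,720 | 6.8% |
| 90 | 0 | 0% |

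These are calendar days that satisfy a definition, not observed follow-up and not events.

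**4. Do the reported counts look as if all such events were included?** Let f be the share of udenafil-treated subjects with the event whose onset falls in the first 90 days (assumed). Expected subjects among the 124 = 124 × incidence × f. Incidences come from the FUEL udenafil arm (Table 25) and from the combined Placebo/De Novo-Udenafil group of the extension (synopsis).

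- Flushing, 14.5% to 15.6%: about 18 to 19 subjects at f = 1, and 9 to 10 at f = 0.5. The placebo arm reports 12 in total. At 15.6%, the binomial probability of 12 or fewer is 0.04 at f = 1 and 0.83 at f = 0.5.
- Headache, 39.0% to 40.5%: about 48 to 50 subjects at f = 1, against 51 reported. That would account for nearly the whole placebo count, unless the same subjects also had headache on placebo.

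Full counting with early onset fits poorly. Partial counting cannot be excluded.

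**5. Routes that remain.**
- Related serious events, reportable at any time (section 9.5.1.2.1).
- Week 30 to 39 calls, if any were made to entrants (Table 2 does not limit them).
- Late entrants. In the synopsis, 14 subjects are 10.9% and 20 are 15.6% of the Udenafil-Udenafil group. The second figure fits only 128 subjects (20/128 = 15.6%), and 14/128 = 10.9%. In the other group 24/173 = 13.9%, and 128 + 173 = 301, the number analysed. Table 5 has 126. Entry after the FUEL count is one possible explanation; such a subject could be in FUEL follow-up as a decliner and then start open-label drug inside the window.

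**6. Leverage.** One subject is 1/200 = 0.5 percentage points. Drug-related serious TEAEs are 2.0% versus 1.0%. As an illustration only, taking one subject out of the placebo count gives 2.0% versus 0.5%, so the difference goes from 1.0 to 1.5 points.

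**The case against.** The strongest reply is that the definition can act only on events in the FUEL dataset, and that FUEL stopped collecting from entrants at Week 26. Section 9.1 gives the later calls to decliners, and the SAP unblinding rule treats Visit 4 as the end for entrants. The 90-day limit matches the decliners' follow-up: Week 39 minus Week 26 is 91 days. The extension made its own adverse event calls and tabulated its events under its own groups. Most of this stands, and it is why wholesale counting is unlikely. It does not close the gap, because a follow-up schedule and an unblinding trigger are not a rule for cutting the dataset, and the routes in step 5 are not covered.

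A reader might infer that the published placebo rates are contaminated for 62% of the arm. The documents do not support that: no event is shown to have been miscounted, and the flushing count argues against full counting. A reader might also infer that the post-letter change opened the window. It shortened one that had no end, and the documents do not say who chose 90 days. Dividing 11,160 by on-treatment days alone (36,540) gives 30.5%, but the window includes post-dose time, so 20.5% is the fairer ceiling.

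Two further points hold. The 126 udenafil entrants fall under the same wording, so both columns could rise; their events are, however, still udenafil events under a udenafil label. And follow-up length, though different between entrants and decliners, is balanced between arms (63% versus 62%), so it does not by itself bias the comparison. The safety analyses are descriptive, so no test or error rate is affected.

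**Conclusion.** The definition has a real gap, and the documents do not show that it changed any count. As written, an event on open-label udenafil within 90 days of the last placebo dose is a placebo TEAE if it reaches the FUEL data, for any of 124 subjects. The ceiling is 20.5% of the nominal placebo window. It rests on no gap before open-label dosing and on reading the last dose as the last randomized one; it is zero at a 90-day gap. The number of events affected cannot be computed, because the documents give no onset dates relative to the first open-label dose. If any were miscounted, the likely net effect is an understated udenafil excess. That matters most for serious events, where counts are small and where reporting at any time leaves a route open. The point deserves a correction to the rule and a check, not a conclusion that the safety tables are wrong.

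**What to change.** Define a TEAE as an event with onset after the first randomized dose and before the earlier of the first open-label extension dose and 90 days after the last randomized dose. Saying randomized for the last dose also removes an ambiguity, since the synopsis calls the extension drug study drug as well.

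Then compare each adverse event onset date in the FUEL dataset with that subject's first open-label dose, and report how many events are removed from each arm, even if the answer is zero. Rerun the affected adverse event and serious adverse event tables only if some are removed. While doing so, reconcile the 126 udenafil entrants of Table 5 with the 128 implied by the synopsis.

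The cost is one clause and a date check. The possible downside for the sponsor is a slightly less favourable safety contrast.

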Source: [Table 14.1.3](#)

Program: [T_14_1_3.sas](#)

The percentage of subjects who discontinued study drug was low and similar between treatment groups (12 [6.0%] of udenafil-treated subjects, 9 [4.5%] of placebo-treated subjects). Six subjects (4 udenafil, 2 placebo) were prematurely discontinued from study drug

by physician decision and 11 subjects (6 udenafil, 5 placebo) were prematurely discontinued from study drug by subject (ie, participant) decision. Three udenafil-treated subjects discontinued study drug due to a serious TEAE and all other subjects discontinued study drug due to other reasons.

The profile of study discontinuations was similar to study drug discontinuations. Subject disposition is summarized in [Table 5](#). Subjects who discontinued from study are identified in [Listing 16.2.1](#), and subjects who discontinued study drug are identified in [Listing 16.2.1.2](#).

Table 5: Subject Disposition

Disposition	Udenafil (N=200) n (%)	Placebo (N=200) n (%)	Total (N=400) n (%)
Randomized and treated	200 (100.0)	200 (100.0)	400 (100.0)
Prematurely discontinued study drug	12 (6.0)	9 (4.5)	21 (5.3)
Lost to follow-up	2 (1.0)	2 (1.0)	4 (1.0)
Physician decision to permanently stop drug	4 (2.0)	2 (1.0)	6 (1.5)
Due to serious TEAE	3 (1.5)	0	3 (0.8)
Due to other reasons	1 (0.5)	2 (1.0)	3 (0.8)
Participant decision to permanently stop drug	6 (3.0)	5 (2.5)	11 (2.8)
Due to other reasons	6 (3.0)	5 (2.5)	11 (2.8)
Discontinued study	12 (6.0)	6 (3.0)	18 (4.5)
Lost to follow-up	7 (3.5)	4 (2.0)	11 (2.8)
Physician decision to discontinue study	1 (0.5)	0	1 (0.3)
Due to serious TEAE	1 (0.5)	0	1 (0.3)
Due to other reasons	0	0	0
Subject decision to discontinue study	4 (2.0)	2 (1.0)	6 (1.5)
Due to other reasons	4 (2.0)	2 (1.0)	6 (1.5)
Completed study ^a	188 (94.0)	194 (97.0)	382 (95.5)
Continued in extension study	126 (63.0)	124 (62.0)	250 (62.5)

TEAE=treatment-emergent adverse event

a As defined by status change form

Source: [Table 14.1.2](#)

Program: [T_14_1_2.sas](#)

